5.6.1 Extent of exposure

Descriptive statistics will be provided for the duration of exposure to the study treatment by weight-categorized dose group for the Initial Treatment Period and the entire study. For all exposure summaries, the “All Participants” column will be a summary of the time from date of first dose through the date of last dose of any treatment, regardless of dose level. Time at risk will be summarized descriptively in the same manner as the duration of exposure.

The cumulative study medication duration will be summarized for participants exposed for given durations of time, and the following categories for duration will be used:

CCI

CCI

Definitions for study medication duration and time at risk in days are provided below. Time at risk will be summarized in years. Time at risk in years is calculated by dividing the time at risk in days by 365.25.

Throughout this section, date of last clinical contact for each participant is defined as the maximum of (last visit date including SFU Visit, last imputed AE start date, date of study termination or completion, last date of study drug administration).

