1.2 Study Design

In this Phase 2, multicenter, randomized, open-label study, the PK, safety, and efficacy of bimekizumab in male and female adolescents (from 12 to <18 years of age) with moderate to severe plaque PSO will be assessed.

The PK, safety, and efficacy of bimekizumab will be evaluated by treating at least 20 participants in each of 2 dose groups (for a total of at least 40 participants evaluable for PK). Both doses are expected to be efficacious based on exposure-response (E-R) predictions. Dose A (320mg every 4 weeks [Q4W] in participants ≥ 65 kg and 160mg Q4W in participants <65kg) is predicted to provide the same systemic bimekizumab exposure as the 320mg Q4W adult dose, and Dose B (64mg Q4W in participants ≥ 65 kg and 32mg Q4W in participants <65kg) is aimed at providing a lower systemic bimekizumab exposure. Weight-based dosing during the Initial Treatment Period will be based on the participant's weight at Baseline.

This study will consist of the following periods:

- Screening Period: up to 5 weeks
- Initial Treatment Period: 20 weeks (5 doses of bimekizumab; administered at Baseline, Week 4, 8, 12, and 16 followed by 4 weeks of observation)
- Open-label Extension (OLE) Period: 104 weeks (bimekizumab administration starts at Week 20 if participant is eligible)
- Safety Follow-up (SFU) Period: 20 weeks after the final dose of bimekizumab

After the Screening Period of up to 5 weeks, eligible participants will be randomized to 1 of the 2 dose groups. The randomization will be stratified by weight category. During the Initial Treatment Period, participants will receive 5 doses of open-label bimekizumab (at Weeks 0 [Baseline], 4, 8, 12, and 16). Participants who complete the Initial Treatment Period, tolerate the treatment, and achieve an IGA response ≤ 2 at Week 20 may continue bimekizumab treatment at the same dose level in the OLE Period.

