5.6.1.1 Initial Treatment Period

Duration of exposure (days):

- $\text{Date of last dose (Initial Period)} - \text{Date of first dose (Initial Period)} + 28$

The use of +28 days reflects the Q4W dosing interval.

Note: If the date of last dose (Initial Period) + 28 extends to a date beyond the date of first dose of the OLE Period:

- $\text{Date of first dose (OLE Period)} - \text{Date of first dose (Initial Period)} + 1$

Note: For participants who die during the Initial Treatment Period: $\text{Date of death} - \text{Date of first dose (Initial Period)} + 1$

Time at risk (days):

For participants who complete the final visit of the Initial Treatment Period and continue to the OLE Period:

- $\text{Date of first dose (OLE Period)} - \text{Date of first dose (Initial Period)} + 1$

Note: For participants who die prior to the final visit of the Initial Period:

- $\text{Date of death} - \text{Date of first dose (Initial Period)} + 1$

Note: If a participant discontinues on or prior to the final visit of the Initial Treatment Period and does not continue to the OLE Period, use the minimum of the following:

- *Total number of days in the Initial Treatment Period (140 days)*

- *Date of last clinical contact – Date of first dose (Initial Period) + 1*

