5.6.1.2 Open Label Extension (OLE) Period

Duration of exposure (days):

Study participants who are enrolled into OLE Period may be allowed dose modification from the Initial Treatment Period. The duration of exposure will be calculated by aggregating distinct dosing periods with respect to each dose level.

The exposure for the i -th dosing period P_i can be calculated as follows:

- *Exposure(P_i) = Last Dose Date of P_i – 1st Dose Date of P_i + min (28, Date of Death – Last Dose Date of P_i)*

Note: If *Last Dose Date of P_i + 28* extends to a date beyond the date of first dose of the next dosing period, then this calculation reverts to:

- *Exposure(P_i) = First Dose Date of P_{i+1} – 1st Dose Date of P_i + 1*

The aggregated exposure for dose level (say A) is the sum of the exposure over all the dosing periods of dose level A:

- *Dose A Exposure = $\sum_{\text{Dose A dosing periods}} \text{Exposure}(P_i)$*

Note: If days between the last dose of P_i and the first dose of P_{i+1} is more than 28 days, then there will be a gap in between the two periods.

Time at risk (days):

For any dosing period P_i before the last dosing period,

- *Time at Risk (P_i) = min (First Dose Date of P_{i+1} , Date of Death) – 1st Dose Date of P_i + 1*

For the last dosing period P_n ,

- *Time at Risk(P_i) = Last Dose Date of P_n – 1st Dose Date of P_n + min (141, Date of Death – Last Dose Date of P_n)*

The aggregated time at risk for dose level is calculated in a similar fashion as the aggregated exposure:

- *Dose A Time at Risk = $\sum_{\text{Dose A dosing periods}} \text{Time at Risk}(P_i)$*

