5.6.1.3 Combined Initial Treatment Period and OLE Period

The combined duration of exposure will be the sum of exposure calculated from the Initial Treatment Period (as defined in Section 5.6.1.1) and OLE Period (as defined in Section 5.6.1.2) for each dose level, minus 1 day. Only the same dose level can be combined within a participant. The time at risk will be calculated similarly.

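### The All Participants exposure column omits the 28-day dosing interval that the dose-level columns include, so one table mixes two quantities and the Initial Treatment Period total is understated

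*SAP*

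**What the plan says.** SAP 5.6.1 plans descriptive exposure statistics by weight-categorized dose group, for the Initial Treatment Period and for the entire study. It sets a rule for the pooled figure, labelled All Participants. The rule opens "For all exposure summaries, the" and states that this "column will be a summary of the time from date of first dose through the date of last dose of any treatment", whatever the dose level. It has no term for the dosing interval.

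The dose-level columns follow other formulas:

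- Initial Treatment Period (SAP 5.6.1.1): last dose minus first dose plus 28 days, capped at death or at the first extension dose. The reason is stated: "The use of +28 days reflects the Q4W dosing interval".
- Open-label extension (SAP 5.6.1.2): "The duration of exposure will be calculated by aggregating distinct dosing periods with respect to each dose level". Each dosing period ends with the smaller of 28 days and the time from last dose to death, or is capped when the next period starts sooner.
- Combined periods (SAP 5.6.1.3): the two exposures are added "for each dose level, minus 1 day. Only the same dose level can be combined within a participant".

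On time at risk, SAP 5.6.1 adds: "Time at risk will be summarized descriptively in the same manner as the duration of exposure".

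**The concern.** A dose given every four weeks is counted as four weeks of exposure in the dose columns. In the pooled column, as written, the last dose counts for nothing, or for one day if both end dates are counted. A reader would expect All Participants to be the pooled version of Dose A and Dose B, and it would not be.

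The sentence is also the only instruction for the pooled column. SAP 5.6.1.2 aggregates by dose level, and 5.6.1.3 combines only within a dose level, so no other rule supplies a total across doses. A programmer who follows the text will produce the shorter figure.

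At stake is the reported amount of adolescent exposure, which readers use to judge how much safety experience the trial provides. A lesser gap in the same sentence is that it does not confine the last dose to the period being summarised. Read literally, the Initial Treatment Period column could run on to an extension dose.

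**Working it through.** The SAP states no exposure total to reproduce. The check applies its date formulas to the planned schedule with no visit-window deviation, taking the pooled last dose within the period summarised.

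Inputs:

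- Initial Treatment Period doses on days 0, 28, 56, 84 and 112 (SAP 1.2: "participants will receive 5 doses of open-label bimekizumab (at Weeks 0 [Baseline], 4, 8, 12, and 16").
- No dose change in that period (Protocol 6.6).
- First extension dose at Week 20, day 140. No dose is given at Week 124 (SAP 5.7.1.1), so the last planned four-weekly dose is at Week 120, day 840.
- At least 40 participants (SAP 3).

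**Initial Treatment Period.** After k on-schedule doses the dose column gives 28(k − 1) + 28 = 28k days. The pooled column gives 28(k − 1), or one day more if counted inclusively.

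| Doses | Dose column (days) | All Participants (days) |
|---|---|---|
| 1 | 28 | 0 or 1 |
| 2 | 56 | 28 or 29 |
| 3 | 84 | 56 or 57 |
| 4 | 112 | 84 or 85 |
| 5 | 140 | 112 or 113 |

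The shortfall is 27 or 28 days throughout. After five doses it is 28/140 = 20%, or 27/140 = 19% if inclusive. If the first extension dose comes three days early, on day 137, the cap gives 137 − 0 + 1 = 138 days in the dose column, still against 112 or 113.

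For 40 participants with five doses, the dose columns sum to 40 × 140/365.25 = 15.33 participant-years. The pooled column gives 40 × 112/365.25 = 12.27, or 40 × 113/365.25 = 12.38 if inclusive.

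With equal arms, the pooled mean before the shortfall lies halfway between the two dose means. A shortfall of 27 or 28 days therefore puts it below both unless they differ by at least 54 to 56 days (2 × 27 to 2 × 28).

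**Entire study, no dose switch.** The extension gives 840 − 140 + 28 = 728 days. Combined, 140 + 728 − 1 = 867 days in the dose column. The pooled column gives 840 or 841. The shortfall is 26 or 27 days, about 3%.

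**Entire study, switch at Week 64 (day 448).**

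- First level: 140 + (420 − 140 + 28) − 1 = 447 days.
- Second level: 840 − 448 + 28 = 420 days.
- Sum 867, pooled 840 or 841. The pooled value is below the sum but well above either level alone.

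**Entire study, switch after a long gap (illustration: last dose on day 168, next on day 280).**

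- First level: 140 + (168 − 140 + 28) − 1 = 195 days.
- Second level: 840 − 280 + 28 = 588 days.
- Sum 783, pooled 840 or 841. The direction reverses.

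**The case against.** The strongest reply is that the sentence is a pooling rule and not a second formula: its purpose is to say that dose level is ignored, and 5.6.1 then says that the definitions of duration follow, with the 28 days in them. That reading is plausible and may be what was meant. But the SAP does not say it. The sentence names its own start and end points, and the Amendment 1 log (SAP 6.4.2) says it was added to give the meaning of this column. Even on the kinder reading, wording that permits a 20% difference needs repair.

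Four stronger inferences are tempting, and the documents do not support them.

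- **That the pooled mean must fall below both dose means over the whole study.** The extension allows weight-category changes and a move to the PS0021 dose, and switchers' exposure is split across dose columns. The examples above show that the direction can go either way.
- **That time at risk also loses its 141-day tail.** For a completer who never switches, that would mean 840 or 841 days instead of 141 + 841 − 1 = 981. But the sentence on time at risk concerns how it is summarised, and 5.6.1.1 to 5.6.1.3 give it separate derivation rules.
- **That exposure-adjusted adverse event rates are wrong.** SAP 5.6.2.1 and 6.1.6.2 divide by time at risk, not by this column.
- **That the cumulative-duration categories shift for the pooled column.** The categories are redacted, so this cannot be checked.

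**Conclusion.** The inconsistency stands for the exposure column. It is firm and systematic in the Initial Treatment Period: 27 or 28 days per on-schedule participant, about 20% after five doses and nearly all of the exposure after one. Over the entire study it is about 3% for participants who never switch dose, and of uncertain direction for those who do.

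The figures assume on-schedule dosing, a literal reading of the sentence with the last dose taken within the period, and no death soon after the last dose, which would shrink the difference. The primary pharmacokinetic analysis is untouched, and no adverse event rate is shown to change. The consequence is a misstated pooled figure in a safety table.

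**What to change.** Replace the sentence in SAP 5.6.1 with an explicit definition:

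- All Participants exposure is the last dose date at any dose level within the period summarised, minus the first dose date in that period, plus 28 days, ignoring dose level and with the same death and next-period caps as the dose columns.
- State that the one-day overlap and dosing gaps are handled as in the dose columns. Without this, the simple formula gives 840 + 28 = 868 days for a participant who never switches, against 867 at dose level. It also gives 868 against a dose-level sum of 783 in the gap example.
- State that overall time at risk follows the end rules of 5.6.1.1 and 5.6.1.2 ignoring dose level, and is not summed across levels. Summing would count switch days twice, because each period before the last adds a day and the correction in 5.6.1.3 works only within a dose level.

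The cost is a few lines of SAP text and a small program change, with no new data. SAP version 3.0 cites database lock among its reasons, so the wording should be settled before outputs are final.

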5.6.1.1 Initial Treatment Period

Duration of exposure (days):

- $\text{Date of last dose (Initial Period)} - \text{Date of first dose (Initial Period)} + 28$

The use of +28 days reflects the Q4W dosing interval.

Note: If the date of last dose (Initial Period) + 28 extends to a date beyond the date of first dose of the OLE Period:

- $\text{Date of first dose (OLE Period)} - \text{Date of first dose (Initial Period)} + 1$

Note: For participants who die during the Initial Treatment Period: $\text{Date of death} - \text{Date of first dose (Initial Period)} + 1$

Time at risk (days):

For participants who complete the final visit of the Initial Treatment Period and continue to the OLE Period:

- $\text{Date of first dose (OLE Period)} - \text{Date of first dose (Initial Period)} + 1$

Note: For participants who die prior to the final visit of the Initial Period:

- $\text{Date of death} - \text{Date of first dose (Initial Period)} + 1$

Note: If a participant discontinues on or prior to the final visit of the Initial Treatment Period and does not continue to the OLE Period, use the minimum of the following:

- *Total number of days in the Initial Treatment Period (140 days)*

- *Date of last clinical contact – Date of first dose (Initial Period) + 1*

5.6.1.2 Open Label Extension (OLE) Period

Duration of exposure (days):

Study participants who are enrolled into OLE Period may be allowed dose modification from the Initial Treatment Period. The duration of exposure will be calculated by aggregating distinct dosing periods with respect to each dose level.

The exposure for the i -th dosing period P_i can be calculated as follows:

- *Exposure(P_i) = Last Dose Date of P_i – 1st Dose Date of P_i + min (28, Date of Death – Last Dose Date of P_i)*

Note: If *Last Dose Date of P_i + 28* extends to a date beyond the date of first dose of the next dosing period, then this calculation reverts to:

- *Exposure(P_i) = First Dose Date of P_{i+1} – 1st Dose Date of P_i + 1*

The aggregated exposure for dose level (say A) is the sum of the exposure over all the dosing periods of dose level A:

- *Dose A Exposure = $\sum_{\text{Dose A dosing periods}} \text{Exposure}(P_i)$*

Note: If days between the last dose of P_i and the first dose of P_{i+1} is more than 28 days, then there will be a gap in between the two periods.

Time at risk (days):

For any dosing period P_i before the last dosing period,

- *Time at Risk (P_i) = min (First Dose Date of P_{i+1} , Date of Death) – 1st Dose Date of P_i + 1*

For the last dosing period P_n ,

- *Time at Risk(P_i) = Last Dose Date of P_n – 1st Dose Date of P_n + min (141, Date of Death – Last Dose Date of P_n)*

The aggregated time at risk for dose level is calculated in a similar fashion as the aggregated exposure:

- *Dose A Time at Risk = $\sum_{\text{Dose A dosing periods}} \text{Time at Risk}(P_i)$*

5.6.1.3 Combined Initial Treatment Period and OLE Period

The combined duration of exposure will be the sum of exposure calculated from the Initial Treatment Period (as defined in Section 5.6.1.1) and OLE Period (as defined in Section 5.6.1.2) for each dose level, minus 1 day. Only the same dose level can be combined within a participant. The time at risk will be calculated similarly.

5.6.2 Adverse Events

Adverse events will be coded according to the MedDRA. Safety Topics of Interest (defined in Section 5.6.2.3) and Safety Topics Closely Monitored (defined in Section 5.6.2.4) will be given special attention in analysis.

Adverse events will be allocated to the respective weight-categorized dose group received. If an AE occurs on the date of a dose switch or on Week 20 dose date, the AE will be attributed to the original dose/period (the “preswitch” dose/period). The only exception to this is for the following type of events, which will be attributed to the new weight-categorized study dose/period:

- Events that fulfill the anaphylaxis criteria for acute events
- Events that fulfill the hypersensitivity reaction criteria
- Events with a high-level term (HLT) of “Administration site reactions NEC”
- Events with an HLT of “Injection site reactions” will be attributed to the dose received at onset

5.6.2.1 General data considerations for AEs

Treatment-emergent AEs are defined as those AEs that have a start date on or following the first dose of IMP through the final dose of study treatment +20 weeks (140 days).

The rules for imputing partial start or stop dates are outlined in Section 5.14.7.5. If it is not possible (due to partial dates) to determine whether an AE is treatment-emergent then it will be assumed to be a TEAE. If the intensity of an AE is unknown, it will be considered as severe. If the relationship to study drug is missing, it will be considered as related.

Treatment-emergent AEs will be summarized as participant incidence (number and percentage of participants experiencing the AE) and AE frequencies (number of AEs including repeat events) by weight-categorized dose group for the Initial Treatment Period, OLE Period, and the combined periods. Treatment-emergent AEs will be attributed to Initial Treatment Period and OLE Period based on duration of exposure definition in Section 5.6.1. For AEs that emerged after 140 days of first dosing but still within the 140 days after last dose window, those AEs will be classified as TEAE but will be excluded from the output based on the Initial Treatment Period. However, these AEs will be included in the AE summaries for Initial Treatment Period and OLE Treatment Period combined.

For AEs that emerged > 140 days after the last dose, these AEs will only be listed in an “All Adverse Events” listing and will not be summarized.

Selected AE summaries will include the exposure-adjusted incidence rate (EAIR) and the exposure-adjusted event rate (EAER). The 95% CIs will be reported for the EAIR only.

The EAIR is the total number of participants with a specific AE divided by the total time at risk across all participants. If a participant has multiple events, the time of exposure is calculated to the first occurrence of the AE being considered with respect to the period being summarized. If a participant has no events, the total time at risk is used. The EAER is the total number of AEs including repeat occurrences in individual participants divided by the total time at risk across all participants with respect to the period being summarized. Exposure adjusted rates (EAIR and EAER) will be scaled to 100 participant-years. Participant time at risk represents the time a participant is at risk for having an AE. These definitions will be used in calculations of exposure-adjusted rates for adverse events.

EAIR in ITP tables should be calculated based on the first occurrence of the AE within ITP. Similarly, EAIR in OLE tables should be calculated based on the first occurrence of the AE

within OLE. For a combined ITP + OLE table, EAIR should be calculated based on the first occurrence of the AE regardless of the period. EAER should include all repeat occurrences within ITP, OLE, or ITP + OLE, depending on the summary. Details of the calculations for exposure adjusted rates (EAIR and EAER) can be found in the Appendix 6.1.6.2.

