5.6 Safety Analysis

Safety variables will be analyzed for all study participants in the SS (for the Initial Treatment Period and combined Initial Treatment Period and OLE Period when needed), and in the OLS (for the OLE Period). In general, safety data that are collected within 140 days of the last study drug dose (covering the 20-week SFU Period) will be attributed to the period in which the participant was before initiating the SFU Period and will be analyzed according to the most recent dose prior to or at the time of the collection.

By-visit tables summarizing safety data should include the SFU visit for the ITP + OLE and OLE summaries. However, SFU should not be included in by-visit safety tables for the ITP alone, since only a few participants will not enter the OLE.

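### Exposure-adjusted AE rates count events and person-time over different windows: two mismatches worth a few percent, and one contradictory attribution rule

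*SAP*

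**What the plan says.** Exposure-adjusted incidence and event rates (EAIR, EAER) divide by time at risk (SAP 5.6.2.1 and 6.1.6.2). The windows are set in several places:

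- **Which events count as treatment-emergent (SAP 5.6.2.1):** from first dose "through the final dose of study treatment +20 weeks (140 days").
- **Period attribution, first rule (SAP 5.6.2.1):** "Treatment-emergent AEs will be attributed to Initial Treatment Period and OLE Period based on duration of exposure definition in Section 5.6.1". Duration of exposure ends 28 days after the last dose: "The use of +28 days reflects the Q4W dosing interval" (SAP 5.6.1.1).
- **Period attribution, second rule (SAP 5.6):** "safety data that are collected within 140 days of the last study drug dose (covering the 20-week SFU Period) will be attributed to the period" the participant was in before follow-up began.
- **Time at risk in the Initial Treatment Period (ITP), participants not entering the OLE (SAP 5.6.1.1):** the smaller of "Total number of days in the Initial Treatment Period (140 days") and the time to last clinical contact.
- **Time at risk in the last OLE dosing period (SAP 5.6.1.2):** first to last dose plus "min (141, Date of Death" minus last dose date). Death is the only event that shortens it. SAP 5.6.1 defines last clinical contact for the whole section, but no OLE formula uses it.
- **Combined periods:** events after day 140 but within 140 days of the last dose are left out of the ITP table. "However, these AEs will be included in the AE summaries for Initial Treatment Period and OLE Treatment Period combined" (SAP 5.6.2.1). Combined exposure is the sum over the two periods minus one day, and "The time at risk will be calculated similarly" (SAP 5.6.1.3). Nothing lifts the 140-day ITP cap.
- **Notation (SAP 6.1.6.2):** the EAIR formula divides by T_Risk, the text beneath it defines T_Exp, and the confidence limits divide by T_Exp.

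**The concern.** A rate per 100 participant-years is interpretable only if each day in the denominator could have produced a counted event, and each counted event fell on a day in the denominator. Here both conditions fail. The combined tables count events from days that are not in the denominator, which pushes the rate up. The OLE tables include days on which nobody was observing the participant, which pushes it down.

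The two attribution rules also cannot both be programmed. Two programmers working from Sections 5.6 and 5.6.2.1 would produce different period tables.

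Exposure adjustment is the stated measure for the selected safety topics of interest (Protocol Section 3; SAP Table 1–1). The same rates appear in the tables of any TEAE, serious TEAEs, and TEAEs leading to withdrawal or to IMP discontinuation (SAP 5.6.2.2). Participants with IGA of 3 or more at Week 20 leave the study. If that is commoner in one dose group, the combined-table effect will differ between the groups.

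**Working it through.** First dose is day 1 and dosing is every 28 days. Under a constant event rate, counting window divided by time at risk is the factor by which the EAER is distorted, and approximately the EAIR for rare events.

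1. **The plan's own figures.** 20 weeks × 7 = 140 days. Five doses give 4 × 28 + 28 = 140 days of exposure. Both match the stated 140. The study maximum of 145 weeks (Protocol 1.1) equals 5 + 120 + 20, which puts the last OLE dose at Week 120.

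2. **Combined table, participant with five doses and no OLE.** The last dose is on day 1 + 16 × 7 = 113. The event window is 113 + 140 = 253 days. Time at risk is 140 days, or 139 after the one-day subtraction. Ratio: 253/140 = 1.81, or 253/139 = 1.82. After three doses: (57 + 140)/140 = 197/140 = 1.41.

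3. **OLE, participant lost at the last dose.** With only the Week 20 dose, 1 day is observed against 141 credited. With the last dose at Week 72, 52 × 7 = 364, so 365 days are observed against 364 + 141 = 505 credited, a ratio of 0.72.

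4. **Cohort of 40.** An OLE completer has 100 × 7 + 141 = 841 OLE days at risk, and 141 + 841 − 1 = 981 combined. A completer's combined event window is also 841 + 140 = 981, so completers are balanced. The affected shares are assumed.

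| Affected | Combined: never enter OLE | OLE: lost at Week 20 dose |
|---|---|---|
| 5% (2) | (2×253 + 38×981)/(2×139 + 38×981) = 1.006 | (2×1 + 38×841)/(2×141 + 38×841) = 0.991 |
| 10% (4) | (4×253 + 36×981)/(4×139 + 36×981) = 1.013 | (4×1 + 36×841)/(4×141 + 36×841) = 0.982 |
| 20% (8) | (8×253 + 32×981)/(8×139 + 32×981) = 1.028 | (8×1 + 32×841)/(8×141 + 32×841) = 0.960 |

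Putting the loss at Week 72 instead gives 0.992, 0.983 and 0.964.

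5. **Attribution rule, conditional.** If the exposure sentence is followed literally, an OLE completer's event window is 700 + 28 = 728 days against 841 at risk: 728/841 = 0.866, so 113/841 = 13.4% of person-time cannot yield a counted OLE event. Events 29 to 140 days after the last OLE dose would belong to no period table. In the ITP, a participant stopping after three doses would have 84 days against 140, a ratio of 0.60. Under Section 5.6 instead, the OLE event window is 700 + 141 = 841 days, or 840 once switch-day events stay in the ITP, against 841. The mismatch is then at most one day.

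**The case against.** The other side has several good points.

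- **The 13% is not established.** A reader might infer that OLE rates will be diluted by 13%. The documents do not support that as a fact. Section 5.6 gives a 140-day rule, and 5.6.2.1 itself leaves only events more than 140 days after the last dose unsummarized. As context, the rationale for SAP Amendment 2 in Section 6.4.1 says time at risk, not exposure, is the relevant quantity for attribution. The exposure sentence is probably a leftover. It is still current text and still contradicts 5.6.
- **Few participants are affected.** SAP 5.6 expects only a few not to enter the OLE, and no planned table isolates them, so the factor of 1.8 is never itself a reported rate. This stands, and it is why the cohort effect is small.
- **The OLE tail is often genuine.** Participants who stop IMP are asked to return 20 weeks after the final dose (Protocol 7.1). Those who do so earn the full tail. Only true loss or refusal creates unobserved time.
- **A late Week 20 dose.** A reader might infer that events between day 140 and a dose given up to three days late fall into neither period. SAP 5.1.1.1.3 runs the ITP to the Week 20 visit, 5.6.1.1 runs time at risk to the first OLE dose, and 5.6.2 keeps events on the dose date in the earlier period. These place such events in the ITP, so the point largely falls away.
- **Importance.** A reader might take exposure-adjusted rates to be the general secondary safety measure. The objectives table attaches the adjustment only to the selected safety topics. Participant incidence and event counts are reported as well and do not use time at risk. No hypothesis is tested.

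None of this repairs the combined-table cap or the missing censoring in the OLE formula.

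**Conclusion.** The concern holds, as a should-fix. Two mismatches exist whichever attribution rule governs:

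- The combined tables count events beyond the time-at-risk cap for participants who never enter the OLE, inflating the cohort rate by roughly 1 to 3%.
- The OLE formula ignores last clinical contact, deflating the cohort rate by roughly 1 to 4%.

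Both ranges assume that 5 to 20% of 40 participants are affected, that everyone else completes to Week 120, and that the event rate is constant. The combined figure takes five doses and an attended follow-up visit; the OLE figure takes loss at the last dose, the extreme case. Effects can be larger within a small weight-categorized dose group.

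The third element is a contradiction to be resolved. Its 13% for an OLE completer is what would follow if the exposure sentence were applied literally, not an expected bias.

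**What to change.** 1. In SAP 5.6.2.1, attribute events to periods by time at risk instead of duration of exposure, and reconcile the sentence with Section 5.6. The day-140 cut in the ITP-only table can stay, because the denominator for participants who do not continue is cut at the same point.
2. In SAP 5.6.1.2, end the last dosing period at the earliest of last dose + 140 days, death, and last clinical contact, counted inclusively. Completers keep the full tail, since last contact includes the follow-up visit.
3. In SAP 5.6.1.3, apply that same end rule to participants who never enter the OLE, in place of the 140-day cap.
4. Keep the switch day in the old period and dose, as SAP 5.6.2 states, apart from its listed exceptions. Ending the window the day before the next period's first dose would create a new mismatch with that rule.
5. In SAP 6.1.6.2, define and use T_Risk throughout, including the confidence limits.

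The cost is SAP wording and one reprogrammed derivation; no new data are needed. OLE rates may rise slightly and combined rates may fall slightly.
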